### 5.3 Sampling and Screening

- End-of-season volunteer recruitment from U17–U19 squads.
- Pre-screening by trained staff; verification with training logs.

### 5.4 Informed Consent

- Written consent from all participants; for those under 18, parental/legal guardian consent obtained.
- Ethics approval: Inonu University Non-Interventional Clinical Research Ethics Committee (Approval No: 2024/5635; Date: 05/03/2024); study conducted in accordance with the Declaration of Helsinki.

## 6. Interventions

- **Conditions:** N0, N25, N45.
- **Nap procedure:** 10-min room adaptation at 13:50 [8]; nap opportunity at 14:00; preferred lying position allowed.
- **Verification:** Sleep onset, duration, and awakening verified via Visual Analogue Scale; wakefulness confirmed in N0 [5,6].
- **Pre-session standards:** Avoid strenuous training for 24 h; avoid alcohol for 24 h and caffeine for 6 h; verbal compliance check at arrival [9–11].
- **Prohibited activities:** No phone use, video games, or visually stimulating tasks during all conditions [12,13].
- **Warm-up standardization:** Light jogging plus a 3-min mobility sequence; heart rate monitored with Polar H10 [7].
- **Testing order:** Pro Agility → 3-min rest → RSA; RPE recorded after each sprint.

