### 4. Setting and Infrastructure

- **Sleep environment:** Isolated, ventilated, dark rooms with blackout curtains; ambient temperature  $\approx 22^{\circ}\text{C}$  [4].
- **Sleep monitoring:** Visual Analogue Scale for sleep–wake verification [5,6].
- **Physiological monitoring:** Polar H10 for heart rate during warm-up [7].

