## 5. Participants

### 5.1 Inclusion Criteria

- Competitive male players from Yeni Malatyaspor U17 or U19 squads.
- Healthy, no recent illness or injury.
- No habitual daytime napping.

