### 7.2 Secondary Outcomes

- **RSA (6×30 m, 20-s recovery):** Best/mean time and fatigue index [15–17].
- **RPE (Borg 6–20):** Recorded after each sprint; session mean used for analysis [18].
- **Hooper Index:** Fatigue, stress, muscle soreness (1–7), sleep quality (1–7) [19].
- **VAS (sleep quality and alertness):** 0–10 cm and 0–100 mm scales [8].

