## 10. Study Workflow and Procedures

1. **Screening and baseline:** Eligibility, informed consent, demographics and anthropometry (SECA stadiometer; Toledo 2096 PP scale;  $\text{BMI}=\text{kg}/\text{m}^2$  [27]). MEQ, PSQI, POMS administered once at baseline [20–22,28].
2. **Pre-session standards:** 24 h no heavy training; 24 h no alcohol; 6 h no caffeine; verbal verification at arrival [9,11,29].
3. **Nap session:** 13:50 adaptation; 14:00 N0/N25/N45; dark quiet room  $\approx 22^\circ\text{C}$ ; subjective verification [5,6]; prohibition of visual/stimulating activities [12,13].
4. **Warm-up:** Light jog plus 3-min mobility; heart rate monitored with Polar H10 for standardization [7].
5. **Performance tests:** 60 min post-awakening [2,3], Pro Agility  $\rightarrow$  3-min rest  $\rightarrow$  RSA (6×30 m, 20-s intervals [15–17]); RPE after each sprint [18].
6. **Post-session:** Hooper and VAS forms [8,19].

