## 11. Data Collection Instruments and Quality Assurance

- **Devices:** SECA® stadiometer; Toledo 2096 PP scale; 16x Polar H10.
- **Validity/reliability:** MEQ, PSQI, POMS are validated instruments [20–22,28]; SmarTracks offers high temporal resolution; literature supports actigraphy-based sleep–wake verification with Fitbit [5,6].
- **Staff training:** Test administrators trained before data collection; measurement repeatability monitored.

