## 18. Budget and Resources (optional)

- **Equipment:** SECA stadiometer, Toledo scale, Polar H10.
- **Consumables and personnel:** Forms, printing, staff time.

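### Sleep timing is called verified, but the only scale defined is a self-rating of sleep quality and alertness, so the data can speak to nap opportunities and not to minutes slept

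*Protocol*

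**What the plan says.** Section 6 makes the claim: "Sleep onset, duration, and awakening verified via Visual Analogue Scale; wakefulness confirmed in N0". Section 4 repeats it under sleep monitoring, naming the "Visual Analogue Scale for sleep–wake verification", and the structured abstract says the same.

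The scale is defined only in Section 7.2, as "VAS (sleep quality and alertness" on a centimetre and a millimetre line. The schedule in Section 7.4 marks the VAS in the T1 column and nowhere else. Step 6 of Section 10 places the "Hooper and VAS forms" after the session. Step 3 of Section 10, the nap session itself, mentions only "subjective verification".

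On validity, Section 11 says that "literature supports actigraphy-based sleep–wake verification with Fitbit". References 5 and 6, cited for the verification in Sections 4, 6, 10 and 11, are by title a review of accelerometer data processing and a comparison of wearable trackers for estimating sleep. The equipment line in Section 18 reads "SECA stadiometer, Toledo scale, Polar H10". The device list in Section 11 holds the same three items.

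The conditions are worded in two ways. The intervention line of the abstract and the nap procedure in Section 6 speak of a nap opportunity. Section 3 and the abstract's background line label the conditions by minutes of nap. Section 3 and Section 10 start testing one hour after awakening.

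**The concern.** The protocol claims a property of the intervention that its instruments, as described, cannot deliver. A rating of how well one slept or how alert one feels is not a time of sleep onset, a duration or a time of waking. The literature cited in support concerns another method.

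This matters because the conditions differ only in length of nap. Section 5.1 requires "No habitual daytime napping", so it cannot be taken for granted that every player falls asleep promptly, or at all, when given 25 or 45 minutes. Section 10 puts the N0 condition in the same dark, quiet room, so dozing in N0 is possible too. Calling sleep verified invites a report to read an N25–N45 difference as an effect of sleep duration, or to read a null result as showing that sleep of that length does nothing. Without a record of sleep, neither reading can be separated from players having slept for less time than the label says, or not at all.

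**Working it through.** The plan gives no figure here to reproduce. The check is to trace each thing said to be verified to the instrument that would record it.

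| Claimed in Section 6 | What the protocol provides | Timed or objective record? |
|---|---|---|
| Onset of sleep | VAS of quality and alertness (7.2), at T1 (7.4); undescribed subjective check (10, step 3) | No |
| Duration of sleep | The same | No |
| Awakening | The same; yet it is the zero point for the test start (3 and 10) | No |
| Wakefulness in N0 | No procedure described | No |

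**Other instruments.** The Polar H10 is assigned to heart rate during the warm-up (Sections 4, 6 and 10), not to the nap period. The Fitbit appears once, in the literature statement in Section 11. It is in neither equipment list, not in the schedule and not in the workflow.

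**Timing of the defined scale.** A player in N25 who wakes at the end of the opportunity wakes at 14:00 + 25 min = 14:25. Testing starts 60 minutes later, at 15:25, and the forms follow the tests. The defined VAS is therefore completed more than an hour after the nap.

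**Size, as illustration only.** The documents give no sleep latency, so it is assumed here. With waking at the end of the opportunity, sleep obtained = opportunity − latency:

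| Assumed latency (min) | Sleep in N25 (min) | Sleep in N45 (min) | Ratio N45:N25 |
|---|---|---|---|
| 0 | 25 | 45 | 1.8 |
| 5 | 20 | 40 | 2.0 |
| 10 | 15 | 35 | 2.3 |
| 15 | 10 | 30 | 3.0 |
| 20 | 5 | 25 | 5.0 |

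Latency may also differ between sessions. A player with latency 0 in N25 and 20 in N45 sleeps 25 − 0 = 25 and 45 − 20 = 25 minutes, so the two conditions do not differ for him in sleep obtained. A latency of 25 minutes or more in N25 means no sleep. A rating of quality or alertness cannot tell these cases apart.

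**The case against.** Several points on the other side are sound and limit the finding.

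- **Some information on sleep may exist.** A reader might infer that nothing in the plan can show whether a player slept. That goes too far. Section 10 places a subjective check inside the nap session, apart from the post-session forms, and Section 4 lists a VAS under sleep monitoring. A self-report can crudely indicate whether a player felt he slept, and the protocol openly calls the check subjective. What is missing is an objective or timed measure.
- **A wearable may have been worn.** A reader might infer from the equipment lists that none was used. The lists do not support that. Section 11 names SmarTracks, and Sections 1 and 9 rely on automated timing, yet no timing system is listed. The lists are therefore incomplete, and Section 18 is headed optional. What can be said is that Sections 4 and 6 do not agree with Section 11.
- **The contrast is already partly framed as opportunity.** The abstract and Section 6 say so. Section 2 sets N25 and/or N45 against N0 and states no hypothesis about minutes slept. The protocol does not itself assert a sleep-dose effect; the word verified only opens the way to one.
- **Loss of power.** A reader might infer that players who do not sleep weaken the trial's power by a calculable amount. The documents give no share asleep, no share dozing in N0 and no effect among sleepers. For a comparison of opportunities, failing to fall asleep is part of the effect being estimated. No power figure is attached to this point.

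None of this rescues the claim that onset, duration and awakening are verified.

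**Conclusion.** The protocol is wrong as written on this point, and it should be corrected. It claims verification of sleep timing and confirmation of wakefulness through a scale that, as defined, rates quality and alertness, and it supports the claim with literature on a method it does not otherwise include.

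The consequence is confined to interpretation. The comparison of nap opportunities in random order remains valid. Statements that players slept 25 or 45 minutes, or that an N25–N45 difference or a null result reflects sleep duration, are not supported by the data the protocol describes. The latency figures only show how far label and sleep could diverge; the conclusion does not rest on them. It rests on the protocol's own definition of the VAS, and it would change if a wearable was in fact used and its records exist.

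**What to change.** Reconcile Sections 3, 4, 6, 7.2, 7.4, 10 and 11, together with the matching line in the abstract.

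- **If no wearable was used:** replace verified and confirmed with self-rated, delete the Fitbit/actigraphy sentence in Section 11 and drop references 5 and 6 as support. Describe the subjective check of Section 10, step 3: what is asked and when. Word conditions, objectives and conclusions throughout as 25- and 45-minute nap opportunities versus none, and say that N25 versus N45 compares lengths of opportunity.
- **If a wearable was used:** list it in Section 11, add it to the Section 7.4 schedule and the Section 10 workflow, and report recorded sleep time by condition descriptively.
- **In either case:** state which recorded time the 60-minute post-awakening start refers to, including in N0, where no awakening is intended. Once verified is removed, that anchor has no stated basis.

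The first option costs only wording; the second adds a descriptive table from data already held. Neither needs a new sample or a new test. The price is a more modest claim about nap duration.

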## 7. Outcomes and Assessment Schedule

### 7.1 Primary Outcome

- **Pro Agility Test time (20-yard shuttle, total 18.28 m):** Provided agility outcomes [14].

### 7.2 Secondary Outcomes

- **RSA (6×30 m, 20-s recovery):** Best/mean time and fatigue index [15–17].
- **RPE (Borg 6–20):** Recorded after each sprint; session mean used for analysis [18].
- **Hooper Index:** Fatigue, stress, muscle soreness (1–7), sleep quality (1–7) [19].
- **VAS (sleep quality and alertness):** 0–10 cm and 0–100 mm scales [8].

### 7.3 Exploratory Outcomes

- **Correlations of PSQI and POMS with performance and subjective measures (Pearson r) [20–23].**

### 7.4 Schedule of Assessments (Timeline)

Time point	Screening	T0 (Baseline)	Intervention	T1 (60 min post-awakening)
Eligibility and consent	X			
MEQ/PSQI/POMS		X		
Nap (N0/N25/N45)			X	
Pro Agility				X
RSA + RPE				X

Time point	Screening	T0 (Baseline)	Intervention	T1 (60 min post-awakening)
Hooper				X
VAS				X

## 8. Sample Size and Justification

- **Software and model:** G\*Power 3.1.9.7; repeated-measures ANOVA (within-subjects, 3 conditions) [24].
- **Parameters:**  $\alpha=0.05$ ,  $1-\beta=0.80$ ; expected effect size  $f=0.30-0.40$  based on prior literature [9,25,26].
- **Result:** Minimum  $\geq 12$ ; **n=16** recruited to accommodate variability and potential attrition.
- **Note:** Crossover design increases power by using each participant as own control [10].

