**Document Date**  
**10 May 2025**

# Strategic Daytime Napping Enhances Agility and Lowers Perceived Exertion but Does Not Improve Fatigue Resistance in Adolescent Soccer Players

## DETAILED TRIAL PROTOCOL

### 1. Structured Abstract

**Background and rationale:** Strategic daytime napping (25 min, 45 min) may acutely influence anaerobic performance in team sports via sleepiness-recovery dynamics.

**Objectives and hypotheses:** Primary objective is to test whether nap conditions improve pro-agility performance. Hypothesis: N25 and/or N45 outperform N0 on pro-agility time. Secondary objectives examine effects on RSA, RPE, Hooper wellness, and VAS alertness/sleep quality. Exploratory objective assesses associations of PSQI and POMS with outcomes.

**Design:** Quasi-experimental, repeated-measures crossover with 3 conditions (N0, N25, N45), 48-h washout, afternoon sessions, testing 60 min post-awakening.

**Participants and setting:** Sixteen competitive male soccer players (U17–U19), isolated dark rooms at  $\approx 22^{\circ}\text{C}$ ; standardized field/lab conditions.

**Interventions:** N0, 25-min, 45-min nap opportunities; sleep–wake verification by Visual Analogue Scale; prohibition of visual/stimulating activities; standardized warm-up monitored by Polar H10.

**Primary/secondary outcomes:** Primary: Pro Agility Test time. Secondary: RSA (6 $\times$ 30 m, 20-s recovery), RPE, Hooper Index, VAS. Exploratory: correlations with PSQI/POMS.

**Sample size:** G\*Power 3.1.9.7 for RM-ANOVA ( $\alpha=0.05$ ,  $1-\beta=0.80$ ,  $f=0.30–0.40$ ) indicated  $\geq 12$ ;  $n=16$  recruited.

**Randomization and blinding:** Within-subject random order of conditions; automated timing to reduce measurement bias; assessor blinding not implemented.

**Statistical analysis (summary):** RM-ANOVA with Bonferroni adjustments; assumption checks (Levene, Mauchly, Greenhouse–Geisser); effect sizes ( $\eta^2$ , Cohen’s  $dz$ , 95% CI); Pearson correlations.

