## 13. Statistical Analysis Plan

- **Software:** SPSS v29.
- **Descriptives:** Mean $\pm$ SD, min–max.
- **Assumption checks:** Normality (skewness/kurtosis within  $\pm 1.5$ ), homogeneity (Levene), sphericity (Mauchly; Greenhouse–Geisser corrections if violated).
- **Primary analysis:** RM-ANOVA across N0–N25–N45; Bonferroni where appropriate.
- **Effect sizes:**  $\eta^2$  (small  $<0.06$ ; medium  $0.06–<0.14$ ; large  $\geq 0.14$ ) and Cohen’s dz for pairwise comparisons; 95% CIs [10,30].
- **Secondary analyses:** RM-ANOVA for RSA metrics, RPE, Hooper, and VAS with appropriate corrections.
- **Exploratory analyses:** Pearson correlations between PSQI/POMS and outcome variables [23].
- **Missing data and sensitivity:** Pre-specified sensitivity checks reported.
- **Pre-specified subgroups:** None; all participants classified as intermediate chronotype (MEQ) [20,28].

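### Does a single minimum of 12 for effect sizes f = 0.30 to 0.40 leave the trial's 16 players short of power at the low end?

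*Protocol*

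**What the plan says.** Protocol section 8 (Sample Size and Justification) names G*Power and the model, "repeated-measures ANOVA (within-subjects, 3 conditions"), with alpha 0.05 and power 0.80. The effect size is given as a range: "expected effect size $f=0.30-0.40$ based on prior literature". The result is a single line: "Minimum $\geq 12$ ; n=16 recruited to accommodate variability and potential attrition". A note adds the general point about crossover efficiency: "Crossover design increases power by using each participant as own control". The Structured Abstract (section 1) repeats the outcome: the calculation "indicated $\geq 12$ ; $n=16$ recruited".

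Section 13 (Statistical Analysis Plan) sets the matching primary analysis, "RM-ANOVA across N0–N25–N45; Bonferroni where appropriate", and provides for sphericity failure with "Greenhouse–Geisser corrections if violated". It also plans Cohen's dz for pairwise comparisons and 95% confidence intervals.

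Neither section 1 nor section 8 states which f gave 12, the correlation among conditions, or the epsilon.

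**The concern.** For a fixed correlation and epsilon, the required number rises steeply as f falls. One number therefore cannot be the smallest sample with 80% power at both f = 0.30 and f = 0.40. The natural suspicion is that 12 is the answer at the favourable end and is presented as if it covered the whole range.

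If so, the four extra players, described as "recruited to accommodate variability and potential attrition", would be a margin only near f = 0.40. At f = 0.30 even 16 completers would fall below 0.80, and any dropout would lower power further. A null finding could then reflect too few players, and a reader could not tell from the document whether that was so. Because section 13 allows for a sphericity correction, epsilon = 1 cannot be taken for granted either.

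**Working it through.** **Inputs from the protocol (section 8).** One group, m = 3 conditions, alpha 0.05, target power 0.80, f from 0.30 to 0.40, stated minimum 12, recruited 16.

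**Assumed, because not stated.** Correlation rho among conditions (0.3 to 0.75 examined) and epsilon (1, with 0.75 as a variant).

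**Formula (within-subjects repeated-measures ANOVA, G*Power's default effect-size definition).** Power = P(F' > Fcrit), where F' is noncentral F with df1 = (m − 1)·eps, df2 = (N − 1)(m − 1)·eps and lambda = f²·N·m·eps/(1 − rho). Fcrit is the 95% point of the central F on the same df.

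**Step 1. Reproduce 12.** Take f = 0.40, rho = 0.5, eps = 1.
- N = 12: lambda = 0.16 × 12 × 3/0.5 = 11.52, df 2 and 22, Fcrit 3.44, power 0.816.
- N = 11: lambda = 0.16 × 11 × 3/0.5 = 10.56, df 2 and 20, Fcrit 3.49, power 0.773.

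The minimum is exactly 12.

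**Step 2. Same inputs across the range.** Required N is 20 at f = 0.30, 15 at f = 0.35 and 12 at f = 0.40. For N = 16 (df 2 and 30, Fcrit 3.32):

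| f | lambda | power at N = 16 |
|---|---|---|
| 0.30 | 0.09 × 48/0.5 = 8.64 | 0.706 |
| 0.35 | 0.1225 × 48/0.5 = 11.76 | 0.839 |
| 0.40 | 0.16 × 48/0.5 = 15.36 | 0.926 |

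With these inputs 16 players reach 0.80 from f of about 0.33 upward.

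**Step 3. Is 12 also possible at f = 0.30?** Take rho = 0.72, eps = 1.
- N = 12: lambda = 0.09 × 36/0.28 = 11.57, power 0.818.
- N = 11: power 0.775.

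The minimum is again exactly 12, now at the lower end. N = 16 gives lambda = 0.09 × 48/0.28 = 15.43 and power 0.927 at f = 0.30.

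**Step 4. All values of f that could lie behind 12.** For each f, find the correlations at which the required N is exactly 12 (power at least 0.80 at N = 12 and below 0.80 at N = 11; eps = 1). Then read off the power of 16 players at f = 0.30.

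| f behind the 12 | rho needed | power of 16 at f = 0.30 |
|---|---|---|
| 0.40 | 0.48–0.53 | 0.69–0.73 |
| 0.37 | 0.56–0.60 | 0.76–0.80 |
| 0.36 | 0.58–0.62 | 0.78–0.83 |
| 0.35 | 0.60–0.64 | 0.81–0.85 |
| 0.30 | 0.71–0.735 | 0.92–0.94 |

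This is a continuum, and the shortfall of about 0.7 is its worst end. The line is crossed at rho = 0.595: above that, 16 players have at least 0.80 power at f = 0.30.

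**Step 5. Does epsilon matter?** Hardly, once N = 12 is held fixed, because a smaller epsilon has to be paired with a larger correlation. At eps = 0.75, 12 at f = 0.40 needs rho 0.585–0.62, and 16 players have 0.70–0.74 at f = 0.30. Likewise 12 at f = 0.30 needs rho 0.77–0.785, and 16 players have 0.92–0.94.

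**Step 6. Cost of a fixed correlation.** Required N at f = 0.30 and f = 0.40 (eps = 1) is 27 and 16 at rho 0.3, 20 and 12 at rho 0.5, and 13 and 8 at rho 0.7. The ratios are 1.69, 1.67 and 1.63, so the premise of the concern is arithmetically right. What does not follow is that the printed 12 is wrong.

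**The case for a change.** The strongest case for acting is that three inputs to a named calculation are missing from the very section that reports it, so this is not something deferred to another document. The same printed text is compatible with power of about 0.69 or 0.94 at the protocol's own lower effect size. The match at f = 0.40 with correlation 0.5 and epsilon 1 makes the unfavourable reading plausible, and under it a few losses would bite: at rho = 0.5 and f = 0.30, 16 completers give 0.71, 14 give 0.64 and 12 give 0.56. The document's title already announces no gain in fatigue resistance, so power for a null is of real interest. Naming the inputs would cost a sentence.

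The omission stands as a fact, and so do the figures. Three things do not. First, both sections give 12 as a floor and do not claim 80% power at 12 for every f in the range; that claim would in fact be true if 12 was computed at f = 0.30. Secondly, a shortfall needs both that 12 came from near the top of the range and that the true effect is near the bottom; neither is shown. Thirdly, a null is weighed by the estimate and its 95% confidence interval, which section 13 already provides, and the planning inputs do not alter that interval. Fatigue index is in any case a secondary outcome in section 7.2. Section 2 does name fatigue resistance in its primary objective, but section 8 ties its calculation to no particular outcome.

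**Conclusion.** No change to the plan is needed. The protocol omits the f, correlation and epsilon behind its minimum of 12, so a reader cannot verify which calculation was run. The figure itself is reproduced under ordinary inputs at the top of the range, and under a higher but still possible correlation at the bottom. Power for 16 players at f = 0.30 therefore lies anywhere from about 0.69 to 0.94, depending on inputs the document does not give; at f = 0.40 it is above 0.91 in every reading examined.

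These figures rest on the noncentral-F calculation for the overall three-condition test, epsilon 1 (little changed at 0.75) and 16 completers. They do not cover the pairwise comparisons.

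Supplying the inputs would make the justification easier to audit. It would not alter the number of players, who are described as already recruited, the primary analysis, or how a positive or null result is read. This is a gap in reporting detail, not an error in the design.

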## 9. Randomization, Allocation Concealment, and Blinding

- **Randomization:** Within-subject random assignment of condition order.
- **Allocation concealment:** Condition order not disclosed to participants until session day; administered by study staff.
- **Blinding:** Participant blinding is infeasible; automated timing reduces measurement bias; assessor blinding not implemented.
- **Unblinding:** Not applicable.

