### 3. Study Design

- **Design:** Quasi-experimental, repeated-measures crossover.
- **Conditions:** N0 (no nap), N25 (25 min), N45 (45 min).
- **Order:** Randomized within participant.
- **Washout:** 48 h between sessions [1].
- **Timing:** Nap starts at 14:00; testing begins 60 min post-awakening [2,3].
- **Testing flow:** Warm-up → Pro Agility → 3-min rest → RSA; RPE after each sprint.

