## 17. Timeline and Gantt Plan

- **Preparation (Months 0–1):** Ethics approval, device calibration, staff training, pilot tests.
- **Data collection (Months 2–3):** Three sessions per participant, 48-h washout.
- **Analysis (Months 3–4):** Data cleaning, statistical analyses, sensitivity checks.
- **Reporting (Months 4–5):** Manuscript and supplementary materials.

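### Condition order is random within each player, but no balancing of orders over the three sessions is specified and the planned RM-ANOVA names no session term, which costs precision with 16 players

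*Protocol*

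**What the plan says.** Section 9 gives the randomisation rule as "Within-subject random assignment of condition order", and Section 3 gives the order as "Randomized within participant". The abstract says the same in similar words. None of the three mentions counterbalancing, a Latin square, blocks or a prepared list of orders, and none says that the draw is free of restriction.

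Section 17 plans "Three sessions per participant, 48-h washout". Section 8 sets the number of players at 16, "recruited to accommodate variability and potential attrition". Section 13 plans a repeated-measures ANOVA over the three nap conditions and names neither a session nor a sequence factor.

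**The concern.** Session position could plausibly matter in this trial, for reasons found in the protocol itself:

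- The baseline visit (Sections 7.4 and 10) holds questionnaires and anthropometry only. Session 1 is therefore the first scheduled performance of the agility and repeated-sprint tests.
- Section 5.1 requires "No habitual daytime napping", so the first nap session is unfamiliar too.
- Sessions 2 and 3 each follow a repeated-sprint session by 48 h.

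With three conditions there are six possible orders. If each of 16 players gets an independently drawn order, one condition can easily fall early more often than another. A session effect then enters the N25–N0 and N45–N0 differences of that one trial as chance error, and it enlarges the residual against which the condition effect is tested. What is at stake is precision and power in a small crossover.

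**Working it through.** **Inputs.** 16 players (Section 8); 3 conditions and 3 sessions, hence 6 orders (Sections 3 and 17); analysis by RM-ANOVA on condition (Section 13). Independent, equally likely orders are an assumption, because the protocol does not say how orders are generated.

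**The plan's own figure.** The protocol gives no figure for order balance. Its one calculation, a minimum of 12 players, reproduces at f = 0.40 if a correlation of 0.5 between conditions is assumed: λ = 0.40² × 12 × 3 / (1 − 0.5) = 11.52, power 0.816. It has no bearing on order.

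**Step 1: spread of session position.** For one player, the N25-minus-N0 position difference is ±1 in four orders and ±2 in two. Its mean is 0 and its variance is (4 × 1 + 2 × 4)/6 = 2. Over 16 players the SD of the mean difference is √(2/16) = 0.354 session.

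**Step 2: how often the imbalance is large** (simulation, 200,000 to 400,000 draws):

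| Event under independent draws | Share of trials |
|---|---|
| N25–N0 off by at least 0.5 session | about 19% |
| At least one nap-versus-N0 contrast off by at least 0.5 session | about 32% |
| Session-1 counts of the conditions differ by 4 or more | 54% |
| Session-1 counts differ by 6 or more | 21% |
| All nine condition-by-session counts at 5 or 6 | 1.7% |
| At least one order unused | 30.2% |

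The last row can be checked by hand: 6(5/6)¹⁶ − 15(4/6)¹⁶ + 20(3/6)¹⁶ ≈ 0.3245 − 0.0228 + 0.0003 = 0.302.

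**Step 3: what this costs.** Let performance change by s per session and let σ be the within-player SD. Both are assumed, since the protocol gives neither. Without a session term, the variance of a condition contrast over independent draws is (2σ² + 2s²)/16, so the session effect inflates it by the factor 1 + s²/σ². With s = 1%:

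- σ = 2%: factor 1 + 1/4 = 1.25.
- σ = 1%: factor 1 + 1 = 2.

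**Step 4: error rate and power of the overall test.** All figures take s = 1% per session. Power also assumes that both naps shift the outcome by one within-player SD.

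| Orders and analysis | Type I error, σ = 2% / 1% | Power, σ = 2% / 1% |
|---|---|---|
| Independent draws, no session term | about 5% / 5% | about 0.70 / 0.48 |
| Balanced list, no session term | about 2.5% / 0.3% | no gain / a loss |
| Balanced list with session term | 5% / 5% | about 0.79 / 0.79 |

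The middle row arises because balance takes the session effect out of the contrasts while the residual still carries it.

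**Step 5: what balance is possible with 16.** Use each order twice (12 players), then two orders and their reversals for the last four. Every mean position difference is then 0. The session-1 counts are 6/5/5 and the session-2 counts 4/6/6. With a session term, the variance of a condition contrast rises by at most 1.2% over exact balance, against about 7% on average (95th percentile 24%) under independent draws.

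**The case against.** Four objections deserve an answer.

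- **The protocol does not say the draw is unrestricted.** This stands. Random order within player is compatible with a prepared, permuted list. A reader might infer simple randomisation from the silence, but the documents support only the statement that no balancing scheme is named. The figures for independent draws are conditional on that reading.
- **Random order already protects the comparison.** This stands as far as it goes. A reader might infer that session effects bias the nap contrasts or produce false positives. They do not: over the randomisation the contrasts are unbiased, and simulated type I error of the planned test stayed at 4.9–5.2% over the session effects tried (up to 2% per session). An assumed 1% per session with a 0.5-session imbalance shifts a contrast by 0.5%, but its standard error is already √(2/16) × 2% = 0.7% at an assumed SD of 2%. The loss is one of precision.
- **A balanced list neither removes the problem nor comes free.** This also stands. Sixteen is not a multiple of three or six. The proposed list cancels a linear session trend, but a pure session-1 effect still meets counts of 6/5/5. Exclusions under Section 5.2 can upset the balance. Used alone, the list makes the planned test conservative. A session term alone would deal with most of the imbalance, at about 7% in variance, so the list is the smaller part of the remedy.
- **Session effects are speculative.** The protocol gives no figure, and the 48-h washout and the 24-h limit on strenuous training address residual fatigue in part. They do not address practice or a first nap.

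**Conclusion.** The point holds as one of efficiency and of incomplete specification. As written, the protocol names neither a balanced order scheme nor a session term. Under independent draws, marked imbalance is common: about 32% of trials have a nap contrast off by half a session or more. Any session effect then goes partly into the contrasts as chance error and partly into the residual. The size of the loss depends on a session effect that the protocol does not give. At an assumed 1% per session and a within-player SD of 1–2%, power is about 0.48–0.70 where 0.79 was attainable. If there is no session effect, almost nothing is lost. The documents do not support a finding of systematic bias, an inflated false-positive rate or an invalid comparison. If a separate analysis plan already includes a session factor, only the order list remains open.

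**What to change.** 1. **Sections 3 and 9.** State that players are allocated at random to a prepared list of the six orders: each order twice, with two orders and their reversals for the last four players, and the list randomly permuted.
2. **Section 13.** Add session (1, 2, 3) as a factor beside condition and player, for example in a linear mixed model. Make this change together with the first, since balancing alone leaves the session effect in the residual.
3. **Report** the realised session-by-condition counts, after any exclusions.

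**Cost.** A new list and a few sentences, with no added visits or players. The session factor takes 2 residual degrees of freedom (30 to 28 with complete data from 16 players). The last orders on the list become slightly more predictable to staff. That matters little here, because assessors are unblinded and timing is automated. Balance will be near-exact, not exact; exact balance over all six orders needs 12 or 18 players.

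**If the sessions are complete,** which the title (worded as a result) and the description of 16 players as recruited suggest, the list can no longer be changed. Then add the session term, say when that was decided, and publish the session-by-condition counts.
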